8.5 Compliance with Dosing

Site staff will review concomitant medication use at each visit.

Patients will be provided with a study drug compliance diary to document BID dosing for 14 days. Patient compliance with dosing will be assessed by in-office review of study drug compliance diary. Patients who miss more than 25% of their study drug doses (*more than* 7 total doses) will be considered non-compliant with dosing and a protocol deviation should be recorded.

8.6 **Patient Disposition**

8.6.1 Completed Patients

A completed patient is one who has not been discontinued from the study and continues study assessments through Visit 6 (Day 21).

8.6.2 Discontinued Patients

Patients may be discontinued from the study prior to their completion of the study due to any of the following reasons:

- AEs
- Protocol violations
- Lack of efficacy
- Administrative reasons (e.g., inability to continue, lost to follow up)

- Sponsor termination of study
- Voluntary withdrawal
- Pregnancy:

If a female has a positive pregnancy test during the study, the patient should stop study treatment, and the Investigator will notify the sponsor immediately. The Investigator shall request copies of all related medical reports during the pregnancy and shall document the outcome of the pregnancy from the patient and/or patient's physician. The Investigator will retain these reports together with the patient's source documents and will provide a copy of all documentation to the sponsor.

• Other

Note: In addition, any patient may be discontinued for any sound medical reason.

Notification of a patient's discontinuation of study drug administration and the reason for discontinuation will be made to CRO and study Sponsor and will be clearly documented on the eCRF. Patients who receive escape medication are to discontinue study drug administration and are to remain in the study and be followed per the protocol to the end of the study. Patients who discontinue study drug administration for other reasons are encouraged to remain in the study and continue with study assessments through the end of the study.

Notification of a patient's discontinuation of study participation and the reason for discontinuation will be made to CRO and study Sponsor and will be clearly documented on the eCRF.

8.7 Study Termination

The study may be stopped at any time by the Investigator or the Sponsor with appropriate notification.

8.8 Study Duration

An individual patient's participation in the study is expected to last approximately 7 weeks from screening to exit.

8.9 Monitoring and Quality Assurance

During the course of the study a CRO monitor, or designee, will make routine site visits to review protocol compliance, assess study drug/device accountability, and ensure the study is being conducted according to the pertinent regulatory requirements. The review of the patients' medical records will be performed in a manner that adequately maintains patient confidentiality. Further details of the study monitoring will be outlined in a monitoring plan.

Regulatory authorities of domestic and foreign agencies, the Sponsor, and/or its designees may carry out on-site inspections and/or audits which may include source

data checks. Therefore direct access to the original source data will be required for inspections and/or audits. All inspections and audits will be carried out giving consideration to data protection as well as patient confidentiality to the extent that local, state, and federal laws apply.

9 ADVERSE EVENTS (AEs)

9.1 Adverse Event

An AE is defined as any untoward medical occurrence associated with the use of a drug in humans, whether or not the event is considered drug-related. An AE can therefore be any unfavorable and unintended sign (e.g., an abnormal laboratory finding), symptom, or disease occurring after the first dose of study drug, without any judgment about causality. Any pre-existing medical condition that worsens after first administration of the study drug will also be considered a new AE. The AE reporting period ends upon study exit. Study drug includes the investigational drug under evaluation and placebo given during any stage of the study.

Documentation regarding the AE should be made as to the nature, date of onset, end date, severity, relationship to study drug, action(s) taken, seriousness, and outcome of any sign or symptom observed by the physician or reported by the patient upon indirect questioning.

9.1.1 Severity

Severity of an AE is defined as a qualitative assessment of the degree of intensity of an AE as determined by the Investigator or reported to him/her by the patient. The assessment of severity is made irrespective of relationship to study drug or seriousness of the event and should be evaluated according to the following scale:

- *Mild*: Event is noticeable to the patient, but is easily tolerated and does not interfere with the patient's daily activities.
- *Moderate*: Event is bothersome, possibly requiring additional therapy, and may interfere with the patient's daily activities.
- *Severe*: Event is intolerable, necessitates additional therapy or alteration of therapy, and interferes with the patient's daily activities.

9.1.2 Relationship to Study Drug

The relationship of each AE to the study drug should be determined by the Investigator using these explanations:

- *Suspected*: A reasonable possibility exists that the study drug caused the AE.
- *Not Suspected*: A reasonable possibility does not exist that the study drug caused the AE.

Suspected adverse reaction means any AE for which there is a reasonable possibility that the study drug caused the AE. "Reasonable possibility" means there is evidence to suggest a causal relationship between the study drug and the AE. Types of evidence that would suggest a causal relationship between the study drug and the AE include: the event follows a reasonable temporal sequence from the time of study drug administration, and/or, follows a known response pattern to the study drug, but could have been produced by other factors; a reasonable temporal sequence of the event with study drug administration exists and, based upon the known pharmacologic action of the drug, known or previously reported adverse reactions to the drug or class of drugs, or judgment based on the investigator's clinical experience, the association of the event with study drug administration seems likely; a single occurrence of an event that is uncommon and known to be strongly associated with drug exposure (e.g., angioedema, hepatic injury, Stevens-Johnson Syndrome); one or more occurrences of an event that is not commonly associated with drug exposure, but is otherwise uncommon in the population exposed to the drug (e.g., tendon rupture); an aggregate analysis of specific events observed in a clinical trial (such as known consequences of the underlying disease or condition under investigation or other events that commonly occur in the study population independent of drug therapy) that indicates those events occur more frequently in the drug treatment group than in a concurrent or historical control group.

9.2 Serious Adverse Events (SAEs)

An AE is considered serious if, in the view of either the Investigator or Sponsor, it results in any of the following regulatory outcome definitions:

- 1. Death;
- 2. A life-threatening AE;
 - Note: An AE is considered "life-threatening" if, in the view of either the Investigator or Sponsor, its occurrence places the patient or patient at immediate risk of death. It does not include an AE that, had it occurred in a more severe form, might have caused death.
- 3. Inpatient hospitalization or prolongation of existing hospitalization;
 - Note: The term "inpatient hospitalization" refers to any inpatient admission (even if less than 24 hours). For chronic or long-term inpatients, inpatient admission includes transfer within the hospital to an acute/intensive care inpatient unit. Inpatient hospitalization does not include: emergency room visits; outpatient/same-day/ambulatory procedures; observation/short stay units; rehabilitation facilities; hospice facilities; nursing homes; or clinical research/Phase 1 units.
 - Note: The term "prolongation of existing hospitalization" refers to any extension of an inpatient hospitalization beyond the stay anticipated or
required for the reason for the initial admission as determined by the Investigator or treating physician.

- 4. A persistent or significant incapacity or substantial disruption of the ability to conduct normal life functions;
 - Note: An SAE specifically related to visual threat would be interpreted as any potential impairment or damage to the patient's eyes (e.g., hemorrhage, retinal detachment, central corneal ulcer or damage to the optic nerve).
- 5. A congenital anomaly/birth defect;
- 6. Important medical event.
 - Note: Important medical events that may not result in death, are lifethreatening, or require hospitalization may be considered serious when, based upon appropriate medical judgment, they may jeopardize the patient or patient and may require medical or surgical intervention to prevent one of the outcomes listed in this definition.

9.3 **Procedures for Reporting AEs**

All AEs and their outcomes must be reported to the study Sponsor or designee, and the IRB/IEC as required by the IRB/IEC, federal, state, or local regulations and governing health authorities and recorded on the appropriate eCRF. AEs should be reported from the first instillation of study drug until the final study visit.

9.3.1 Reporting a Suspected Unexpected Adverse Reaction

All AEs that are 'suspected' and 'unexpected' are to be reported to CRO, the study Sponsor and the IRB/IEC as required by the IRB/IEC, federal, state, or local regulations and governing health authorities.

9.3.2 Reporting an SAE

To ensure patient safety, all SAEs, regardless of relationship to the study drug, must be immediately reported (i.e. no later than 24 hours after the site's awareness of the event). All information relevant to the serious AE must be recorded on the appropriate CRFs. The Investigator is obligated to pursue and obtain information requested by CRO and the Sponsor in addition to that information reported on the eCRF. All patients experiencing an SAE must be followed up and the outcome reported.

In the event of an SAE, the Investigator must notify the Sponsor or designee immediately (i.e. no later than 24 hours after the site's awareness of the event); obtain and maintain in his/her files all pertinent medical records, information, and medical judgments from colleagues who assisted in the treatment and follow-up of the patient; provide CRO and the study Sponsor with a complete case history, which includes a statement as to whether the event was or was not suspected to be related to the use of the study drug; and inform the IRB of the AE within their guidelines for reporting SAEs.

Contact information for reporting Serious AEs:

9.4 Procedures for Emergency Unmasking of Study Drug

With each shipment of study drug, sites will also receive one emergency unmasking envelope for every study drug kit received. The envelopes and kits will both be labeled with the same 5-digit study drug kit number. The envelopes are sealed and contain the unmasked treatment information for the corresponding study drug kit.

Envelopes should be stored in a secured location and should only be opened (i.e., breaking the randomization code for that patient) in the event of a medical emergency, or when knowing the treatment assignment is absolutely necessary for the medical management of the study patient. When possible (i.e., in non-emergent situations), the study sponsor or representative should be notified prior to unmasking study drug. In emergency situations, the investigator must notify the sponsor within 24 hours after determining that it is necessary to unmask the treatment assignment. If the investigator determines that emergency unmasking is necessary, the investigator should identify and retrieve the emergency unmasking envelope for the given patient. The emergency unmasking envelope should be opened by the designated site personnel. The investigator must also indicate in source documents and in the eCRF that the mask was broken and provide the date, time, and reason for breaking the mask. Any AE or SAE associated with breaking the mask must be recorded and reported as specified in this protocol.

Patients should have their study drug discontinued immediately if treatment assignment is unmasked.

9.5 Type and Duration of the Follow-up of Patients after AEs

The Investigator will follow unresolved AEs to resolution until the patient is lost to follow-up or until the AE is otherwise explained. Resolution means the patient has returned to baseline state of health or the Investigator does not expect any further improvement or worsening of the AE. If the patient is lost to follow-up, the Investigator should make 3 reasonable attempts to contact the patient via telephone, post, or certified mail. All follow-up will be documented in the patient's source document. Non-serious AEs identified on the last scheduled contact must be recorded on the AE eCRF with the status noted.

If the Investigator becomes aware of any new information regarding an SAE (i.e., resolution, change in condition, or new treatment), a new SAE/Unanticipated Report Form must be completed and faxed to the Sponsor or designee within 24 hours of the site's awareness of the event. The original SAE form is not to be altered. The report should describe whether the event has resolved or continues and how the event was treated.

10 STATISTICAL HYPOTHESES AND METHODS OF ANALYSES

10.1 Study Populations

10.1.1 Intent-to-Treat Population

The Intent-to-Treat (ITT) population consists of all patients who are randomized. All data will be included and no patients will be excluded because of protocol violations. The ITT population will be analyzed as randomized and will be used for the efficacy analyses.

10.1.2 Safety Population

The Safety population includes all randomized patients who received at least one dose of investigational treatment. The Safety population will be analyzed as treated and will be used for the safety analyses. No data will be excluded for any reason.

10.1.3 Per Protocol Population

The Per Protocol (PP) population is a subset of the ITT population and includes patients who remain in the study through Visit 5 (Day 15) with no major protocol violations that would affect the assessment of the primary efficacy endpoints of the study. Patients without major protocol violations thought to affect the primary efficacy outcome who discontinue the study due to lack of efficacy will be analyzed in the PP analysis with missing data after discontinuation imputed as failures for success/failure endpoints and will be imputed using last observation carried forward (LOCF) for other endpoints. Otherwise, this population will be analyzed as treated using observed data only for confirmatory analyses.

10.2 Unit of Analysis

The unit of analysis in this study will be the study eye for all efficacy and safety summaries. Additionally, non-ocular AEs will be presented at the patient level. Non-study eye safety summaries will also be presented as appropriate.

10.3 General Imputation Methods

The primary analyses of all efficacy data will use LOCF to impute missing data; data for visits after a patient is discontinued for lack of efficacy will be imputed as

failures for success/failure endpoints and will be imputed using LOCF for other endpoints. To check robustness of results, sensitivity analyses of the primary efficacy data will include analyses of observed data only, imputing data from patient visits after discontinuation for lack of efficacy as failures. Other imputation methods may be applied as additional sensitivity analyses.

Per Protocol analyses will use observed data only, with the exception of patients who have missing data due to discontinuation for lack of efficacy; for these patients, missing data after discontinuation will be imputed as failures.

10.4 Efficacy Variables

The primary efficacy variables are:

- 3. Absence of anterior chamber cells (i.e., score of '0') at Visit 5 (Day 15) for:
 - a. The 1.0% concentration of RTA 408 Ophthalmic Suspension compared to placebo
 - b. The 0.5% concentration of RTA 408 Ophthalmic Suspension compared to placebo.
- 4. Absence of pain (i.e., score of '0') at Visit 3 (Day 4) for:
 - c. The 1.0% concentration of RTA 408 Ophthalmic Suspension compared to placebo; to be tested if 1a. is statistically significant in favor of the active arm.
 - d. The 0.5% concentration of RTA 408 Ophthalmic Suspension compared to placebo; to be tested if 1b. is statistically significant in favor of the active arm.

Secondary efficacy variables include:

- 1. Absence of anterior chamber cells at Visits 3, 4, or 6 (Days 4, 8 or 21 respectively)
- 2. Absence of pain at Visits 4, 5 or 6 (Days 8, 15 or 21 respectively)
- 3. Absence of flare at Visits 3, 4, 5 or 6 (Days 4, 8, 15 or 21 respectively)

10.5 Safety Variables

The safety variables are:

- Slit Lamp Examination
- Pin-hole Visual Acuity
- Intraocular Pressure
- Dilated indirect ophthalmoscopic examination
- AEs

10.6 Statistical Hypotheses

H₀₁₁: The difference, between study eyes treated with the 1.0% concentration of RTA 408 Ophthalmic Suspension and study eyes treated with placebo, in

the proportion of study eyes with absence of anterior chamber cells (score of 0) at Visit 5 (Day 15) = 0.

- H_{A11}: The difference, between study eyes treated with the 1.0% concentration of RTA 408 Ophthalmic Suspension and study eyes treated with placebo in the proportion of study eyes with absence of anterior chamber cells (score of 0) at Visit 5 (Day 15) \neq 0, with superiority claimed if the difference is greater than 0 (RTA 408 Ophthalmic Suspension Placebo).
- H_{012} : The difference, between study eyes treated with the 0.5% concentration of RTA 408 Ophthalmic Suspension and study eyes treated with Placebo, in the proportion of study eyes with absence of anterior chamber cells (score of 0) at Visit 5 (Day 15) = 0.
- H_{A12}: The difference, between study eyes treated with the 0.5% concentration of RTA 408 Ophthalmic Suspension and study eyes treated with placebo in the proportion of study eyes with absence of anterior chamber cells (score of 0) at Visit 5 (Day 15) \neq 0, with superiority claimed if the difference is greater than 0 (RTA 408 Ophthalmic Suspension Placebo).

and

- H₀₂₁: The difference, between study eyes treated with the 1.0% concentration of RTA 408 Ophthalmic Suspension and study eyes treated with placebo in the proportion of study eyes with absence of pain (score of 0) at Visit 3 (Day 4) = 0.
- H_{A21}: The difference, between study eyes treated with the 1.0% concentration of RTA 408 Ophthalmic Suspension and study eyes treated with placebo in the proportion of study eyes with absence of pain (score of 0) at Visit 3 (Day 4) \neq 0, with superiority claimed if the difference is greater than 0 (RTA 408 Ophthalmic Suspension Placebo).
- H₀₂₂: The difference, between study eyes treated with the 0.5% concentration of RTA 408 Ophthalmic Suspension and study eyes treated with placebo in the proportion of study eyes with absence of pain (score of 0) at Visit 3 (Day 4) = 0.
- H_{A22}: The difference, between study eyes treated with the 0.5% concentration of RTA 408 Ophthalmic Suspension and study eyes treated with placebo in the proportion of study eyes with absence of pain (score of 0) at Visit 3 (Day 4) \neq 0, with superiority claimed if the difference is greater than 0 (RTA 408 Ophthalmic Suspension Placebo).

The primary analyses will first test the difference in the proportion of patients with absence of anterior chamber cells in the study eye between the 1.0% concentration of RTA 408 Ophthalmic Suspension and placebo and between the 0.5% concentration of RTA 408 Ophthalmic Suspension and placebo at Visit 5 (Day 15) using the Pearson chi-squared statistic.

If the proportion of patients with a grade of '0' for anterior chamber cells is statistically significantly higher for the 1.0% concentration versus placebo at a 1-

sided alpha=0.10, then the hierarchical hypothesis testing will compare the proportion of patients with absence of ocular pain at Visit 3 (Day 4) between the 1.0% concentration of RTA 408 Ophthalmic Suspension and placebo using the Pearson chi-squared statistic at a 1-sided alpha=0.10.

If the proportion of patients with a grade of '0' for anterior chamber cells is statistically significantly higher for the 0.5% concentration versus placebo at a 1-sided alpha=0.10, then the hierarchical hypothesis will compare the proportion of patients with absence of ocular pain at Visit 3 (Day 4) between the 0.5% concentration of RTA 408 Ophthalmic Suspension and placebo using the Pearson chi-squared statistic at a one-sided alpha=0.10.

Additionally, 95% confidence intervals will be constructed around the difference in proportions for each primary outcome using asymptotic normal approximations. Fisher's exact tests will be employed in cases of expected counts less than five.

If the test of the difference in the proportion of study eyes with absence of anterior chamber cells is statistically significant in favor of the 1.0% or 0.5% concentration of RTA 408 Ophthalmic Suspension versus placebo, then the study will be considered a success and the concentration(s) of RTA 408 Ophthalmic Suspension showing statistical significance will be declared to be superior to placebo in the proportion of study eyes with absence of anterior chamber cells at Visit 5 (Day 15).

10.7 Sample Size

10.8 Methods of Analyses

Summaries for continuous variables will include the sample size (n), mean, standard deviation, median, minimum, and maximum. Minima and maxima will be reported with the same precision as the raw values; means, standard deviations, and medians will be presented to one additional decimal place than reported in the raw values. Summaries for discrete variables will include frequencies and percentages. All percentages will be rounded to one decimal place (i.e., XX.X%). Differences between treatment groups will be calculated as Test – Placebo and change from baseline will be calculated as follow-up visit – baseline. The baseline visit will be defined as the last non-missing measure prior to initiation of investigational treatment.

All efficacy analyses will use a one-sided alpha=0.10 test unless otherwise stated. All summaries will be presented by treatment group and where appropriate by visit.

10.9 Demographics and Baseline Medical History

Patient demographics: gender, race, ethnicity, and age will be presented using discrete summary statistics. Age will also be presented using continuous summary statistics.

Non-ocular and ocular (study eye and fellow eye) medical history will be summarized by treatment group using discrete summaries.

10.10 Primary Efficacy Analyses

The primary efficacy variables, study eyes with absence of anterior chamber cells at Visit 5 (Day 15) and study eyes with absence of pain at Visit 3 (Day 4), will be summarized using discrete summary statistics, including 90% asymptotic normal confidence intervals for each treatment group. The primary efficacy analyses will first test the difference in proportion of study eyes with a grade of '0' in anterior chamber cells between the 1.0% concentration of RTA 408 Ophthalmic Suspension and placebo and between the 0.5% concentration of RTA 408 Ophthalmic Suspension and placebo at Visit 5 (Day 15) using the Pearson chi-squared statistic.

If the proportion of patients with a grade of '0' for anterior chamber cells is statistically significantly higher for the 1.0% concentration versus placebo at a 1-sided alpha=0.10, then the hierarchical hypothesis testing will compare the proportion of patients with absence of ocular pain at Visit 3 (Day 4) between the 1.0% concentration of RTA 408 Ophthalmic Suspension and placebo using the Pearson chi-squared statistic at a 1-sided alpha=0.10.

If the proportion of patients with a grade of '0' for anterior chamber cells is statistically significantly higher for the 0.5% concentration versus placebo at a 1-sided alpha=0.10, then the hierarchical hypothesis will compare the proportion of patients with absence of ocular pain at Visit 3 (Day 4) between the 0.5% concentration of RTA 408 Ophthalmic Suspension and placebo using the Pearson chi-squared statistic at a one-sided alpha=0.10.

Additionally, 95% confidence intervals will be constructed around the difference in proportions for each primary outcome using asymptotic normal approximations. Fisher's exact tests will be employed in cases of expected counts less than five.

If the test of the difference in the proportion of study eyes with absence of anterior chamber cells is statistically significant in favor of the 1.0% or 0.5% concentration of RTA 408 Ophthalmic Suspension versus placebo, then the study will be considered a success and the concentration(s) of RTA 408 Ophthalmic Suspension showing statistical significance will be declared to be superior to placebo in the proportion of study eyes with absence of anterior chamber cells at Visit 5 (Day 15).

Additionally, a Cochran-Armitage test will be used to test for trend separately in the proportion of study eyes with absence of anterior chamber cells and the proportion of study eyes with absence of pain with increasing active concentration, using all three treatment groups.

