5 STUDY POPULATION

5.1 Number of Patients

Approximately 105 patients will be enrolled in this multi-center study, 35 per arm, in order to complete 31 patients per arm.

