8.1.5 Methods for Assignment to Treatment Groups

All patients screened for the study who sign a consent form will be assigned a 3-digit screening number which will be entered in the Screening and Enrollment Log. The Patient ID number will be a 7-digit number consisting of the 4-digit site number combined with the 3-digit screening number.

Once a patient meets all qualification criteria, they will be randomly assigned to masked treatment using a 1:1:1 (0.5% RTA 408: 1.0% RTA 408: placebo) assignment ratio. Patients will be randomized on the first day post-surgery (Day 1) by assignment of the lowest 5-digit study drug kit number available at their investigative site. No study drug kit numbers will be skipped or omitted. A trained, unmasked technician will administer study drug from the bottle of the study drug kit assigned to the patient. Each study drug kit will be labeled with the 5-digit study drug kit number. The bottle of study drug will be dispensed to the patient for use on subsequent days.

8.2 **Concurrent Therapies**

The use of any concurrent medication, prescription or over-the-counter, used within the last 60 days before Visit 1 and for the duration of the study is to be recorded on the patient's source document and corresponding case report form (eCRF) along with the reason the medication was taken.

Concurrent enrollment in another investigational drug or device study is not permitted.

8.2.1 Prohibited Medications/Treatments

Prohibited medications/treatments for the duration of the study are:

- Topical ocular corticosteroid in the study eye
- Topical ocular NSAID in the study eye
- Systemic corticosteroids
- Periocular injection of any corticosteroid solution in the study eye
- Corticosteroid depot in the study eye (after implantation)
- Topical ocular cyclosporine in the study eye
- Anti-inflammatory or immunomodulating agents systemically, or in the study eye.

- Systemic medications for benign prostatic hyperplasia (BPH) (e.g., tamsulosin, silodosin, alfuzosin, finasteride).
- Systemic Analgesics/pain relievers, including opioids, narcotics and other pain medications systemically (e.g., gabapentin, pregabalin, NSAIDs and opioids).

Note: Use of acetaminophen (up to 4,000 mg/day) and 'baby' aspirin (up to 81 mg/day) during the study are allowed. Use of an opioid during cataract surgery is allowed.

- Glaucoma medications or ocular hypertension medications in the study eye
- Contact lens or a collagen shield in the study eye

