14.1 Primary Analysis

The anterior chamber cell grade for all study eyes will be recorded as well as the anterior chamber cell count if the actual number of cells observed is 10 cells or fewer (only white blood cells should be counted; red blood cells and pigment cells should not be counted). The 5-unit grading scale for anterior chamber cells is from 0 to 4 where 0 = 0 cells, 1 = 1 to 10 cells, 2 = 11 to 20 cells, 3 = 21 to 50 cells and 4 = >50 cells.

Ocular pain will be assessed by the patient utilizing a Numerical Pain Rating Scale (NPRS) graded from 0 to 10. Patients will assess the level of pain they are experiencing in the study eye at the time of the assessment.

[figure not shown]
The examiner will ask the patient the following question in reference to Figure 1 and will record the number selected by the subject on the appropriate eCRF.

Statistical Analysis Plan Protocol RTA 408-C-1307

Version 1.0

On a scale of 0 to 10, in which 0 is no pain and 10 is the worst possible or unbearable pain, please mark on the scale the number that best describes the pain or discomfort you are feeling in the operated* eye at this time. The middle of the scale (around 5) can be used to describe "moderate pain".

The proportion of study eyes with absence of anterior chamber cells and the proportion of study eyes with absence of ocular pain will be presented overall and by treatment group using categorical summary statistics, including 90% confidence intervals.

Additionally, 80% and 95% confidence intervals will be constructed around the difference in proportions for each primary outcome using asymptotic normal approximations. Pearson's chi-square tests will be employed for statistical inference testing. Fisher's exact tests and exact confidence intervals will be employed in cases of expected counts less than five.

Additionally, a Cochran-Armitage test will be used to test for trend separately in the proportion of study eyes with absence of anterior chamber cells and the proportion of study eyes with absence of pain with increasing active concentration, using all three treatment groups.

The ITT population will be used for the primary analyses. In addition, confirmatory analyses will be performed on the PP population. The primary analysis variables will be presented in patient listings.

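### The asymptotic normal intervals for the primary proportions fall modestly short of their stated coverage at 35 per arm; named score-type intervals would come closer on average

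*Protocol*

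**What the plan says.** Protocol 10.10 presents the two primary proportions "including 90% asymptotic normal confidence intervals for each treatment group". For the treatment difference it adds: "Additionally, 95% confidence intervals will be constructed around the difference in proportions for each primary outcome using asymptotic normal approximations". In sparse tables the protocol switches the test to Fisher's exact test but says nothing about the interval.

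SAP 14.1 widens the set for differences: "80% and 95% confidence intervals will be constructed around the difference in proportions for each primary outcome using asymptotic normal approximations". It also has a sparse-data clause that reaches intervals: "Fisher's exact tests and exact confidence intervals will be employed in cases of expected counts less than five". For the 90% per-arm intervals the SAP names no method, so it is unclear whether they are asymptotic as in the protocol and whether the exact clause applies to them.

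The testing level is set in protocol 10.8: "All efficacy analyses will use a one-sided alpha=0.10 test unless otherwise stated". Protocol 10.10 and SAP section 5 define success by the test on anterior chamber cells, not by any interval.

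**The concern.** For a single proportion, the asymptotic normal (Wald) interval is centred on the observed rate and takes its standard error from that same rate. With 35 eyes per arm, both features and the discreteness of the binomial pull attained coverage away from the nominal figure, usually downwards. The exact clause in the SAP applies only when an expected count is below five, so it leaves most of the plausible range of response rates untouched.

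At stake are the per-arm rates and differences that will be read off the tables as the main estimates from a dose-ranging trial. A 90% or 95% label should be about right on average. Separately, Fisher's test in the fallback uses only part of the one-sided 0.10 that the sponsor has allowed itself, which costs power when response is rare or nearly universal.

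**Working it through.** **Inputs.** Protocol 5.1: "Approximately 105 patients will be enrolled in this multi-center study, 35 per arm, in order to complete 31 patients per arm"; 3 × 35 = 105 and 3 × 31 = 93, so the counts agree. The primary analysis is ITT with missing values filled in (SAP 6.3, 14.1), so the denominator is about 35 per arm. The plan states nominal levels only and no attained coverage or size, so there is no figure of its own to reproduce. The sample-size sections give no response rates in the available text; rates are scanned as assumptions.

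**Per-arm 90% interval.** With x successes of n = 35, p̂ = x/n and z = 1.645, Wald is p̂ ± z√(p̂(1−p̂)/n). Coverage at true rate p is the sum of binomial(35, p) probabilities over the counts whose interval contains p.

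Worked case, p = 0.25:
- 5/35 has upper limit 0.240, so it misses. 6/35 has upper limit 0.1714 + 1.645√(0.1714 × 0.8286/35) = 0.276, so it covers.
- 13/35 has lower limit 0.237, so it covers. 14/35 has lower limit 0.264, so it misses.
- Coverage = P(6 ≤ X ≤ 13) = 86.6%.

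The same sum gives 90.5% at 0.20, 89.9% at 0.30, 88.1% at 0.40 and 91.1% at 0.50.

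| 90% per arm, true rates 0.2 to 0.8 | Mean | Minimum |
|---|---|---|
| Wald | 88.3% | about 83% |
| Wilson | 90.0% | 86.2% |

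**Width is not the cause.** Let a = z²/n = 2.706/35 = 0.0773. Wilson is narrower than Wald when (p̂(1−p̂) + a/4)/(1+a)² < p̂(1−p̂), that is when p̂(1−p̂) > 1/(4(2+a)) = 0.1203. At 5/35 the product is 0.1429 × 0.8571 = 0.1224, above the threshold; at 4/35 it is 0.1143 × 0.8857 = 0.1012, below. So Wilson is the narrower interval for 5 to 30 successes. Widths, Wald against Wilson: 0.222 v 0.219 at 7/35; 0.272 v 0.263 at 14/35. The shortfall comes from centring and discreteness.

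**Difference intervals.** Wald is (p̂₁ − p̂₂) ± z√(p̂₁(1−p̂₁)/35 + p̂₂(1−p̂₂)/35), with coverage summed over all 36 × 36 = 1,296 tables and both true rates between 0.15 and 0.85:

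| Level | Wald mean (range) | Newcombe mean |
|---|---|---|
| 95% | 94.0% (91.6 to 94.8%) | 94.9% (minimum 93.3%) |
| 80% | 78.9% (74.9 to 81.7%) | 79.6% |

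**If only 31 per arm contribute.** The picture is similar: per-arm Wald mean 87.9% and 95% difference mean 94.0%, both for rates 0.15 to 0.85.

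**Sparse-table test.** At 35 v 35 the smallest expected count is half the total successes (or failures), so Fisher is used when the pooled rate is below 10/70 = 14.3% or above 85.7%. Unconditional one-sided size at nominal 0.10:

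| Null rate | Fisher alone | Planned Pearson/Fisher rule | P(Fisher used) |
|---|---|---|---|
| 5% | 0.025 | 0.025 | over 99% |
| 10% | 0.053 | 0.062 | 84% |
| 15% | 0.058 | 0.084 | 38% |
| 20% | 0.059 | 0.095 | 8% |
| Maximum over all rates | 0.066 | 0.104 | |

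Putting Boschloo's test into the fallback (reject when the Fisher p-value is at most 0.141) raises the power of the whole rule from 44% to 51% at 5% v 15%, and from 57% to 65% at 85% v 97%. The maximum size of the combined rule is 0.104 before and after, because it arises in the Pearson part.

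**The case against.** The case for leaving the plan alone is fair in several respects.

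- **The shortfall is small.** It is about 2 points on average per arm and about 1 point for differences, in summaries that decide nothing. This stands and sets the weight of the point.
- **Wilson is not uniformly better.** It too falls below 90% at some rates. At 0.30 it covers only for counts 7 to 14, giving 86.2%, where Wald (counts 7 to 15) gives 89.9%. Its advantage is in the average and in a less severe worst case. This stands.
- **The SAP already turns to exact intervals in sparse tables.** This stands for differences. If the clause is also read as covering the per-arm intervals (Clopper-Pearson below five successes or failures, Wald otherwise), mean coverage is 96.2% for rates 0.05 to 0.15 and 89.8% for 0.15 to 0.85, but the minimum in the latter range is still 84.1%. The protocol has no such clause, and the SAP does not say which reading is meant.
- **Fisher's conservatism is not an error.** Alpha is an upper bound and it is respected. At 20% v 40% Fisher is almost never used, and power is 72% with the planned rule or with Pearson alone.

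Four stronger readings are tempting and are not supported. A reader might infer that the per-arm intervals are too narrow; the width comparison shows otherwise. A reader might infer that the tests miss their level in sparse data; they only lose power. A reader might infer that dose choice depends on these intervals; neither document states such a rule. Finally, the unpooled 80% interval can exclude zero when the pooled Pearson test does not reject, as at 14/35 v 9/35. A reader might take that as a threat to the decision, but it is uncommon (about 0.5 to 2% in the scenarios checked) and success follows the test.

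**Conclusion.** The point holds as a minor one about reporting. At 35 per arm, the asymptotic intervals miss their nominal coverage by about 2 points on average per arm and about 1 point for differences, mostly outside the region that the SAP's exact clause reaches. Score-type intervals bring the averages close to nominal. The documents also leave the per-arm method open in the SAP and differ on the sparse-case interval.

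The success decision and its error rate are unaffected, and no figure in the plan is shown to be wrong. The coverage averages weight all true rates in the stated ranges equally; coverage at any single rate may be better or worse. The Fisher question is secondary: a loss of power confined to pooled rates below 14.3% or above 85.7%. Whether this trial would be in that region cannot be judged from the available text.

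**What to change.** In protocol 10.10 and SAP 14.1, name Wilson intervals for each arm's 90% interval and Newcombe or Miettinen-Nurminen intervals for the 80% and 95% differences. State that they apply to sparse and non-sparse tables alike. This also settles the difference between the two documents on the sparse-case interval.

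As an option, replace Fisher's exact test in the fallback with Boschloo's unconditional exact test and keep the one-sided Pearson test elsewhere. Describe the combined rule as having a maximum size of 0.104, the same as the current plan, rather than as guaranteeing 0.10.

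The cost is a software option and a line of text in each document. Endpoints, sample size and alpha do not change. Per-arm intervals will shift toward 50% and will be wider only for counts near 0 or 35 (fewer than 5 or more than 30 of 35).
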